4.2 Number of subjects

Subjects will be recruited from up to 15 study sites in the USA. Approximately 280 subjects will be included in the study.

4.3 Duration of subject participation

A subject may be involved in the study for approximately 15.0 months from screening to the final follow-up visit. “End of study” is defined as the time point when the last subject has completed the last study visit.

4.4 Randomization and blinding

[REDACTED]

4.4.2 Blinding

Investigator blinding will be accomplished by using a Treating Investigator to administer the treatments and a Blinded Evaluator, to whom randomization and treatment are concealed, to conduct the blinded assessments. The Blinded Evaluator is not allowed to discuss treatments with the Treating Investigator or subjects. All study related documents that contain information regarding the treatment of subjects should not be available to the Blinded Evaluator. Safety assessments will be performed by non-blinded personnel as treatment-related AEs are expected to occur during a few days after treatment, thereby revealing which subjects has received the study product.

4.4.3 Emergency unblinding

Not applicable as the Treating Investigator is unblinded.

4.5 Medical history

History of surgical events, medical conditions (including any prior dermatological procedures or implants), and medications taken prior to screening shall be documented using medical terminology.

4.6 Concomitant medications, treatments, and procedures

Except as noted below, concomitant medications or other treatments or procedures may be utilized when the Investigator or his/her authorized designee considers it medically necessary. Information regarding any use of concomitant medications, including prescription and over-the-counter medications administered during the investigation is to be recorded. The generic name or the trade name of all concomitant medication or a description of the procedure and the reason for its use shall be documented.

The following medications, treatments, and procedures are restricted or prohibited during the study:

- [REDACTED]
- [REDACTED]
- [REDACTED]
- [REDACTED],
- [REDACTED]
- [REDACTED]
- [REDACTED]
- [REDACTED]
- [REDACTED]
- [REDACTED]

If a treated subject has used any of the above prohibited medications or procedures he or she should, for safety reasons, continue in the study for the scheduled follow-up visits.

4.7 Schedule of events

A horizontal bar chart consisting of 15 black bars of varying lengths. The bars are arranged in two main groups: a top group of 5 bars and a bottom group of 10 bars. The bars in the top group are relatively short, while the bars in the bottom group are much longer, with the longest bar reaching nearly the bottom of the frame.

Term	Percentage
Climate change	92
Global warming	100
Green energy	88
Carbon footprint	85
Sustainable development	82
Renewable energy	78
Emissions reduction	75
Green economy	72
Carbon tax	95

4.8.18 Unscheduled Visits

- When necessary, unscheduled visits could take place (in particular because of an AE needing a specific treatment). Unscheduled visits related to the study should be documented and all adverse events captured.

5. Subjects

5.1 Subject information and informed consent

The Investigator or his/her authorized designee must always use the IRB-approved subject information and informed consent form and it must not be changed without prior discussion with the Sponsor and approval from the applicable IRB.

It is the responsibility of the Investigator or his/her authorized designee to give each subject prior to inclusion in the study, full and adequate verbal and written information regarding all aspects of the clinical study that are relevant to the subject's decision to participate throughout the study, e.g. explain the purpose and procedures of the study, the duration and number of expected participants, possible risks involved, and the opinion of the IRB. The subject shall be informed that the participation is confidential and voluntary and that the subject has the right to withdraw from the study at any time, without any effect on his/her future medical care, treatment or benefits to which the subject is otherwise entitled. The information shall be provided in a language clearly and fully understandable to the subject. The subject shall be given sufficient time to read and understand the informed consent form and to consider participation in the study. Before any study-related activities are performed, the informed consent form shall be personally signed and dated by the subject and the Investigator or his/her authorized designee responsible for conducting the informed consent process.

All original signed informed consent forms shall be filed in the Investigator file. The subject shall be provided with a copy of the signed and dated informed consent form and any other written information.

The Investigator shall ensure that important new information is provided to new and existing subjects throughout the study.

5.2 Inclusion criteria

The subjects must meet the following criteria to be eligible for the study:

1. Subjects willing to comply with the requirements of the study and providing a signed written informed consent.
2. Males or non-pregnant, non-breastfeeding females, 22 years of age or older.
3. Subjects seeking augmentation therapy for the lips.

5.3 Exclusion criteria

The presence of any of the following exclusion criteria will exclude a subject from enrollment in the study:

1. Known/previous allergy or hypersensitivity to any injectable HA gel or to gram positive bacterial proteins.

2. History of allergy or hypersensitivity to lidocaine or other amide-type anesthetics, or topical anesthetics or nerve blocking agents (if such products are intended to be used for that subject).

5.4 Screening and subject numbers

Prior to any study procedures being conducted, the subject must sign the informed consent form. The subject number will be assigned at Baseline / Day 1. All study procedures performed should be documented in the subject's source documents and in the electronic Case Report Forms (eCRFs). The subject number, subject name and other information sufficient to link the eCRF to the medical records (e.g. national identification number, chart number, etc.) should be recorded.

A screen failure is a subject who signed informed consent but never enrolled (i.e. received treatment) in the study. For screen failures, the subject's source documents should indicate which assessments have been made and the reason why the subject was discontinued.

A subject is considered enrolled when they have signed the informed consent and are randomized and/or treated.

During the study conduct, the Blinded Evaluators shall not have access to any subject's source documents that identify the subject.

5.5 Withdrawal of subjects

Each subject shall be advised in the informed consent form that the subject has the right to withdraw from the study at any time, for any reason, without prejudice. Subjects may also be discontinued from this study if the Investigator determines that it is in the subject's best interest to do so, and may be withdrawn at the Investigator's discretion at any time.

The reason and date for withdrawal should be documented in the subject's source documents and eCRFs. When possible, an explanatory comment should be added to further explain the reason for withdrawal. If withdrawal of a subject occurs during a regular investigational visit, the eCRF for that specific visit should be completed as far as possible.

If withdrawal of a subject occurs between regular study visits the subject should, when possible (irrespective of the reason for withdrawal) be scheduled for a termination visit to document subject outcome for the primary and secondary endpoints.

If a subject is withdrawn from the study, all data collected until the time of withdrawal will be used in the analyses.

Subjects who receive product and are withdrawn or discontinued from the study will not be replaced.

For AEs still ongoing at the time of the withdrawal, see Section [8.7.6](#).

6. Study Products

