Effective date: 2017-08-17 12:21

Effective

Version: 4.0

 GALDERMA	Title 43USK1701 CIP	Doc id [REDACTED]
---	-------------------------------	----------------------

A Randomized, Controlled, Evaluator-Blinded, Multi-Center Study to Evaluate the Effectiveness and Safety of *Restylane® Kysse* versus a Control in the Augmentation of Soft Tissue Fullness of the Lip

Study product: *Restylane® Kysse*

Comparator product: [REDACTED]

Clinical trial number (CTN): 43USK1701

Sponsor: [REDACTED]

Investigators and Study Administrative Structure

Sponsor:

Q-Med AB, a Galderma affiliate

Galderma Research and Development, LLC

Medical Expert:

Clinical Project Manager:

Study Statistician:

Further details on all participating Investigators and the complete administrative structure of the study are found in the study files. Note that administrative changes are to be documented in the study files without requiring a clinical investigational plan (CIP) amendment.

Sponsor Signatures

The CIP is electronically signed in the document management system within the Q-Med AB quality management system by the representatives listed below.

[REDACTED]

[REDACTED] [REDACTED]

[REDACTED] [REDACTED]

[REDACTED]

[REDACTED]

[REDACTED] [REDACTED] [REDACTED]

[REDACTED]

[REDACTED]

[REDACTED]

Synopsis

Title of study:	A randomized, controlled, evaluator-blinded, multi-center study to evaluate the effectiveness and safety of Restylane® Kysse versus a control in the augmentation of soft tissue fullness of the lip
Clinical Trial Number:	43USK1701
Countries involved	United States
Number of sites	Approximately 15
Number of Subjects	Approximately 280 randomized subjects. [REDACTED]
Target Indication	Injection into the lips for lip augmentation and for correction of perioral rhytids in subjects over the age of 21.
Primary Effectiveness Objective and Endpoint	1. The primary objective of the study is to demonstrate non-inferiority of Restylane® Kysse versus a control in lip fullness augmentation by comparing change from baseline in the Blinded Evaluator assessment of Medicis Lip Fullness Scale (MLFS) in the upper and lower lip separately, at 8 weeks after last injection.

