Secondary Effectiveness Objectives and Endpoints	1. To evaluate the effectiveness of Restylane® Kysse in lip fullness augmentation based on the Blinded Evaluator assessment of MLFS in the upper and lower lip, using the following endpoints: 
 Change from baseline at 16, 24, 32, 40, and 48 weeks after last injection Response rates (defined as at least 1 point improvement from baseline) at 8, 16, 24, 32, 40, and 48 weeks after last injection. 2. To evaluate the aesthetic improvement of the upper perioral rhytids and oral commissures after treatment with Restylane® Kysse , based on the Blinded Evaluator assessment of Wrinkle Assessment Scale ¹ (WAS), at 8, 16, 24, 32, 40, and 48 weeks after last injection using the following endpoints: 
 Change from baseline Response rates (defined as at least 1 point improvement from baseline). 3. To evaluate the aesthetic improvement (overall appearance)

¹Lemperle, G. A Classification of Facial Wrinkles. Plastic Reconstructive Surgery. 2001:1735-1750.

	
after treatment with Restylane® Kysse, based on the Global Aesthetic Improvement Scale (GAIS) at Week 8, 16, 24, 32, 40, and 48 weeks after last injection using response rates (defined as at least “Improved”).
 
4. Subjects’ satisfaction after treatment with Restylane® Kysse using the FACE-Q scales Satisfaction with Lips and Appraisal of Lines: Lips at Week 8, 16, 24, 32, 40, and 48 weeks.5. Lip fullness compared to baseline, using Central Independent Photographic Reviewer’s assessment of improvement in fullness of each (yes/no) by comparison of random, blinded pairings of the baseline and post-baseline photographs taken at Week 8, 24, 40, and 48.

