Subjects will have in-clinic follow up visits at 2, 4, 8, 16, 24, 32, 40, and 48 weeks after the last injection. If a touch-up is performed, a second 2-week and 4-week follow-up visits should be scheduled. At the 48-week visit after all study procedures for the visit are completed, subjects can receive an optional additional treatment if optimal aesthetic improvement is not maintained with *Restylane® Kysse*. If re-treatment is performed, a second 2-week and 4-week follow-up visits should be scheduled. In addition to the clinic visits, phone visits will also occur as specified in the study flow chart below.

A Study Flow Chart is provided on the next page.

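### Protocol 5.5 does not ask an already-treated subject who leaves before Week 8 to attend the Week 8 assessment, so avoidable gaps in the primary endpoint are imputed or left out

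*Protocol*

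**What the plan says.** The primary endpoint is the change in Blinded Evaluator MLFS, "in the upper and lower lip separately, at 8 weeks after last injection" (Protocol synopsis). The clinic schedule reads: "Subjects will have in-clinic follow up visits at 2, 4, 8, 16, 24, 32, 40, and 48 weeks after the last injection" (Protocol 4.1).

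Protocol 5.5 has two rules for leavers. At a regular visit: "If withdrawal of a subject occurs during a regular investigational visit, the eCRF for that specific visit should be completed as far as possible". Otherwise: "If withdrawal of a subject occurs between regular study visits the subject should, when possible" "be scheduled for a termination visit to document subject outcome for the primary and secondary endpoints". Subjects may leave at any time and "may be withdrawn at the Investigator's discretion at any time". The section adds that the analyses use what was gathered up to withdrawal. It says nothing about a later Week 8 assessment.

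Elsewhere the protocol keeps treated subjects under observation. A user of prohibited treatments should, for safety reasons, "continue in the study for the scheduled follow-up visits" (4.6), and a subject who becomes pregnant after treatment must stay in follow-up (8.7.7).

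On analysis, Protocol 10.6 names hot deck imputation for missing primary data. SAP 2.2 limits PP to ITT subjects who complete Week 8 without an important deviation. SAP 2.4.2 adds a sensitivity analysis on observed cases. SAP 2.1 and 2.4.3 require non-inferiority against 0.5 for both lips in both ITT and PP.

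**The concern.** The injection is given on Day 1, with one possible touch-up. By the time a subject leaves, the randomised treatment has normally been delivered, and leaving the study does not undo it. The Week 8 outcome of such a subject still bears on the ITT question and could be measured at a visit that is already planned. Section 5.5 does not ask for it, and its sentence on data use stops at the date of withdrawal.

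Subjects who leave early because of disappointment or an adverse event may differ from those who stay. If so, hot deck replaces their values with those of subjects who stayed, while PP and the observed-case analysis omit them. Agreement among the three would then be weak evidence that dropout did no harm, because all three draw on the same observed subjects.

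**Working it through.** **1. The plan's own allowance.** SAP 1.1.2 gives 234 evaluable subjects; SAP 2.7 gives about 15% for dropouts and for subjects non-evaluable because of deviations at Week 8.

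- 234 / (1 − 0.15) = 275.3, rounded up to 276. This is consistent with the stated figure of about 280. The inputs behind 234 are redacted, so 234 itself cannot be checked.
- 0.15 × 280 = 42 subjects, which split 2:1 is 28 Kysse and 14 control.
- The 15% includes protocol deviators. A deviator can be excluded from PP and still have an observed Week 8 MLFS in ITT. Within the plan's own allowance, 15% is therefore an upper bound on the missing fraction.

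**2. One subject followed through the analyses.** Take a treated subject who leaves in Week 5 and does not return.

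| Analysis | Source | Treatment of this subject |
|---|---|---|
| ITT, primary | Protocol 10.6 | Week 8 value imputed by hot deck |
| PP | SAP 2.2 | Excluded: Week 8 visit not completed |
| ITT, observed cases | SAP 2.4.2 | Excluded: no Week 8 value |

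A termination visit in Week 5 or 6 changes none of these rows, because no visible text lets that value stand for Week 8.

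**3. Size, as an assumption.** In one arm let μ be the mean change among observed subjects, p the missing fraction, and d the amount by which missing subjects are worse.

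- True arm mean: (1 − p)μ + p(μ − d) = μ − pd.
- Expected arm mean from hot deck with donors in the same arm, or from observed cases: μ.
- Overstatement in that arm: pd.
- Net bias toward Kysse: (pd in Kysse) − (pd in control).

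This assumes that the hot-deck matching variables, which are not visible, do not explain d. The documents give neither p nor d. With d = 0.5 grade where a deficit is assumed, and the same p in both arms:

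| Missing fraction p | Deficit in Kysse only | Same deficit in both arms | Deficit in control only |
|---|---|---|---|
| 5% | 0.05 × 0.5 = 0.025 | 0 | −0.025 |
| 10% | 0.10 × 0.5 = 0.05 | 0 | −0.05 |
| 15% | 0.15 × 0.5 = 0.075 | 0 | −0.075 |

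Against the margin of 0.5, the Kysse-only column is 5%, 10% and 15%. Each missing value replaced by an observed one reduces p, and the bias falls in proportion.

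**The case against.** The strongest objection is that much of the relevant text is hidden. The schedule of events, the visit descriptions and most of Protocol Section 7 are redacted, and early termination (ET) is a listed abbreviation, so an early-termination procedure may exist. This stands against any claim about what is assessed at Weeks 2 and 4. It bears less on the point here, because 5.5 is the section on withdrawal, is readable, and contains no request to return at Week 8.

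A reader might infer that a subject who leaves at the Week 2 or Week 4 visit has no outcome recorded, while one who leaves a day later does. The documents do not support that. The visible endpoints do start at Week 8 (for example "Response rates (defined as at least 1 point improvement from baseline) at 8, 16, 24, 32, 40, and 48 weeks after last injection"), but what is scored earlier is not visible. The between-visit rule is only a request when possible, so it guarantees nothing. From Week 8 onward, completing the visit's eCRF would be expected to capture the endpoints due then.

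A reader might also infer that an unblinded investigator could remove poor responders. The definition of Investigator is broad enough to include the Treating Investigator, who is unblinded (Protocol 4.4.3), but nothing shows that discretion would be used differently by arm.

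It is also fair to say that withdrawal is a right, and that the plan has safeguards: success is needed in both ITT and PP, and there is an observed-case analysis. Both facts stand. The right to leave is respected by a request that can be refused. The safeguards do not address informative dropout, since none of them uses a leaver's own Week 8 value.

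**Conclusion.** The point holds as a gap in data collection. Before Week 8, 5.5 lets a treated subject leave, or be withdrawn at discretion, without being asked for the primary assessment. The visible analyses then all depend on leavers resembling completers, given any redacted matching variables.

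The size is modest and not established by the documents. Under a one-arm deficit of 0.5 grade it is 0.025 to 0.075 for 5% to 15% missing; it vanishes if the deficit is equal in both arms and changes sign if it lies in control alone. The 0.075 should not be read as an estimate: it treats the whole 15% as missing, although that figure includes deviators, and puts the whole deficit in one arm. The case for acting is that the loss is partly avoidable at little cost, not that a large bias has been shown.

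**What to change.** Amend Protocol 5.5 so that, unless the subject withdraws consent to further contact, any treated subject withdrawn before Week 8 is asked to attend the already scheduled Week 8 Blinded Evaluator assessment. State there and in SAP 2.4.2 that this MLFS is the observed Week 8 value in ITT, and extend the sentence on data gathered up to withdrawal to cover it. SAP 2.2 should say whether such a subject counts as having completed Week 8 for PP.

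Subject to the redacted schedule, 5.5 should also say whether the termination assessments apply when a subject withdraws at a visit without endpoint assessments, or refer to the schedule if it already says so. This is a clarification only and does not by itself change the primary analysis.

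The cost is amendment wording with the usual IRB review. The visit and the evaluator are already in place. The downside is that some subjects will decline, so imputation will still be needed for them.

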6.1 Investigational product

The investigational device (i.e. the study product) is *Restylane® Kysse*, manufactured by Q-Med AB (a Galderma affiliate located in Uppsala, Sweden). The sterilized gel contains 20 mg/mL stabilized HA and 3 mg/mL lidocaine hydrochloride in a physiological buffer. Each syringe contains 1 mL gel. The investigational product is for single use only.

6.2 Packaging, labelling, and storage

[REDACTED]

[REDACTED]

[REDACTED]

[REDACTED]

[REDACTED]

6.3 Product accountability

The study products will be released to the Investigator or his/her authorized designee after study approvals have been received from the FDA and IRB and the CTA has been signed by all parties.

The Investigator must ensure that the study products are kept in a secure location, with access limited to those authorized by the Investigator.

The study products must be traceable from the manufacturer to their use in subjects until return or disposal. It is therefore important that the Investigator maintains accurate product accountability records, i.e. documentation of the physical location of all study products, deliveries, and return of study products between the Sponsor and the Investigator, and documentation of administration of product to the subject.

When the study is completed, all unused or expired study product at each study site shall be returned to the Sponsor representative for destruction, or be destroyed locally at the site if documented as agreed with Sponsor.

Any malfunctioning study products shall be reported as described in Section [8.8](#).

Products deliberately or accidentally destroyed during shipment or at a study site shall be accounted for and documented. Used syringes, needles, and any unused material must be discarded immediately after the treatment session and must not be reused due to risk for contamination of the unused material and the associated risks including infections according to standard procedures at the site. Disposal of hazardous material, i.e. syringes and needles must conform to applicable laws and regulations. The study products must not be used outside the study.

6.4 Treatment

When injecting *Restylane® Kysse*, the following techniques may be used in the lip

A large black rectangular redaction box covers the majority of the page content, from approximately y=113 to y=886. The redaction is not perfectly uniform, with some white space visible at the top and bottom edges. There are also a few small white squares located in the bottom right corner of the redacted area.

Term	Percentage
Climate change	100
Global warming	98
Green energy	95
Carbon footprint	92
Sustainable development	88
Renewable energy	85
Emissions reduction	82
Green economy	78
Carbon tax	95

[REDACTED]

[REDACTED]

[REDACTED]

[REDACTED]

[REDACTED]

[REDACTED]

6.4.9 Treatment compliance

Not applicable; the treatment will be administered by the injector at the investigational site.

7. Efficacy Assessments

7.1 General information

The methods for collecting efficacy data are described in the following sections. To minimize inter-observer variability, every effort should be made to ensure that preferably the same individual who made the initial baseline determinations completes all corresponding follow-up evaluations.

[REDACTED]

[REDACTED]

[figure not shown]
[REDACTED]

[REDACTED]

[REDACTED]
[REDACTED]
[REDACTED]
[REDACTED]

[REDACTED]	[REDACTED]	[REDACTED]

8. Safety Assessments

